2.7.3 Handling of missing values/censoring/discontinuations

MMR rates at specific time points: Patients discontinuing the randomized treatment prior to a specific time point due to any reason or patients without an available assessment at that time point will be considered as non-responders for that time point.

MMR rates by specific time points:

Patients without any documented response for which an evaluable response assessment was never provided will be considered as non-responders for the period of time up to that time point.

Molecular response at specific time points: The category “Missing” will be assigned to

- Ongoing cases, i.e. patients without assessment at the specific time point who have not discontinued study treatment and have not been treated sufficiently long for a specific time point
- Discontinued due to progressive disease/death prior to a specific time point
- Discontinued due to other reasons prior to a specific time point
- **Molecular response category by specific time points:** The category “Missing” will be assigned to patients for whom an evaluable response assessment was never provided.

Time to MMR: For patients in the FAS who have not experienced any MMR, the time will be censored as follows in the Kaplan-Meier analysis:

- If a patient does not achieve the specified response before the cut-off date for the analysis, censoring time will be the last molecular assessment (PCR) date on treatment prior to the cut-off date or the EoT visit, whichever comes first.
- If a patient discontinues study treatment prior to achieving a response for a reason other than disease progression or death, then the patient will be censored at the last molecular assessment (PCR) date on treatment prior to the cut-off date or the EoT visit, whichever comes first.
- If a patient discontinues study treatment prior to achieving a response due to progression or death, then the censoring time will be set to the longest follow-up time in the treatment group, that is, consider the response is impossible to reach.
- In case no on-treatment response assessment was performed, the patient will be censored at day 1.

Duration of MMR: For patients in the MMR responder set who have not experienced any event (loss of MMR, progression to AP/BC, or CML-related death), the duration will be censored at the last molecular assessment (PCR) date on treatment.

CCyR rates at specific time points: Patients discontinuing the randomized treatment prior to a specific time point due to any reason will be considered as non-responders for that time point.

CCyR rates by specific time points: This will be handled similarly as MMR, but with CCyR instead.

Cytogenetic response at specific time points: This will be handled similarly as molecular response category.

Cytogenetic response category by specific time points: This will be handled similarly as molecular response category.

Time to CCyR: For patients in the CCyR analysis set who have not experienced any CCyR, the time will be censored in the same manner as Time to MMR.

Duration of CCyR: For patients in the CCyR responder set who have not experienced any event (loss of CCyR, progression to AP/BC, or CML-related death) the duration will be censored at the last cytogenetic assessment date on treatment or the last PCR evaluation on treatment indicating MMR, whichever is the latest.

TTF: For patients in the FAS who have not reached treatment failure, their TTFs will be censored at the time of their last study assessment (PCR, cytogenetic, hematologic or extramedullary) before the cut-off date.

PFS: For patients who have not experienced an event (disease progression to AP/BC or death from any cause), their PFS times will be censored at the date of last study assessment (PCR, cytogenetic, hematologic or extramedullary) before the cut-off date, regardless of subsequent intake of treatment(s) after randomization.

OS: Patients who are alive at the time of the analysis data cutoff date will be censored at the date of last contact (see [Section 2.1.1](#)) before the cut-off date, regardless of subsequent intake of treatment(s) after randomization.

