Safety summaries (tables, figures) on the Safety set (respectively on the Switch Analysis Set) include only data from the on-treatment (resp. on-switched treatment) period with the exception of baseline data which will also be summarized where appropriate (e.g. change from baseline summaries). In particular, summary tables for adverse events (AEs) will summarize only on-treatment (resp. on-switched treatment) events, with a start date during the on-treatment (resp. on-switched treatment) period (**treatment-emergent** AEs) (resp. switched-treatment-emergent AEs). In addition, a separate summary for death including on-treatment and post-treatment deaths will be provided.

However, all safety data (including those from the pre-treatment, post-treatment and post-switched treatment period) will be listed and flagged as appropriate.

Efficacy summaries on the FAS (apart from OS and PFS) include data from baseline up to either the last assessment on or before the EoT visit or before or on treatment failure, whichever is the earliest.

Efficacy summaries on the Switch Analysis Set include data from baseline_switch up to the last assessment on or before the S-EoT visit or before or on treatment failure during the switched treatment period, whichever is the earliest.

The efficacy assessments collected post-treatment failure, post-EoT or post S-EoT visit are not included in any efficacy analyses (except for OS and PFS analyses). However, they will be listed and flagged as appropriate.

Windows for multiple assessments

Data such as molecular response, cytogenetic response collected over time (including unscheduled visits) will be summarized by scheduled time point. As patients do not always adhere to the visit schedule, visits will be remapped according to visit windows defined in Tables 2-1 to Table 2-4 of this document to enable by-visit analysis. Only those protocol-defined visits will have the visit window defined. Each assessment (including the end of treatment assessment), either scheduled or unscheduled, will have a mapped visit assigned, as long as study day is available, according to the defined visit window up to the date with data included.

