2.7.1.2 Cytogenetic response

At each assessment time point the cytogenetic response status of each patient is classified as complete, partial, major, minor, minimal response and none (a review of a minimum of 20 metaphases is required):

- Complete response (CCyR): 0% Philadelphia chromosome positive (Ph+) metaphases
- Partial response (PCyR): >0 to 35% Ph+ metaphases
- Major response (MCyR = CCyR + PCyR): 0 to 35% Ph+ metaphases
- Minor response (mCyR): >35 to 65% Ph+ metaphases
- Minimal response: >65 to 95% Ph+ metaphases
- None: >95 to 100% Ph+ metaphases.

As per protocol, bone marrow aspirate for cytogenetic analyses will be performed as long as subjects have not achieved MMR. Therefore, in case no bone marrow aspirate was performed but the subject is in MMR at a specific time-point, the subject is considered to have achieved CCyR at that time-point. The date of CCyR is imputed by the date of MMR at the same scheduled time-point.

CCyR rates at all scheduled data collection time points, i.e., the protocol-planned visits. Such rates are defined as the proportion of patients in CCyR at the respective time points among patients in the CCyR Analysis Set, which excludes patients who are in CCyR at baseline.

CCyR rates by all scheduled data collection time points, i.e., the protocol-planned visits. Such rates are defined as the proportion of patients who achieve CCyR at or before the respective time points among patients in the CCyR Analysis Set.

Cytogenetic response category at specific time points, i.e., the protocol-planned visits. At each assessment time point the cytogenetic response status of each patient is classified as complete, partial, major, minor, minimal response and none (a review of a minimum of 20 metaphase is required) as defined in Appendix.

Cytogenetic response category by specific time points, i.e., the protocol-planned visits. This is defined as the best (lowest) cytogenetic response category up to the specific time points.

Time to CCyR (in weeks) is defined for patients as: (date of first documented CCyR - date of randomization + 1)/7.

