Duration of CCyR is defined for patients in the CCyR Responder Set as the time between date of first documented CCyR and the end date of CCyR, i.e. the earliest date of loss of CCyR, progression to AP/BC, or CML-related death. Loss of CCyR and progression to AP/BC are defined in Appendix. For patients for whom none of the events above is reported, the duration will be censored (see [Section 2.7.3](#)). The duration of CCyR (in weeks) is calculated as: (end date or censoring date of CCyR - date of first CCyR + 1)/7.

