5.1.2.1 Other imputations

Incomplete date of initial diagnosis of cancer

Missing day is defaulted to the 15th of the month and missing month and day is defaulted to 01-Jan.

Stratum reported in the CRF

This will be derived from the Bone Marrow Aspirate data recorded in the corresponding eCRF pages at baseline. In some case the baseline sample may be missing or not evaluable (i.e. <20 metaphases).

The following imputation rule will be applied to derive the missing or non evaluable values:

- Major cytogenetic response (MCyR) (0 to 35% Ph+ metaphases) will be assumed if BCR-ABL1 levels $\leq 10\%$ (IS).

Rationale:

ELN 2013 recommendations are providing treatment milestones with response categories for cytogenetic and molecular response, which we can refer to for the imputation:

6 mo	BCR-ABL1 <1% and/or Ph+ 0	BCR-ABL1 1-10% and/or Ph+ 1-35%	BCR-ABL1 >10% and/or Ph+ >35%
------	---------------------------------	---------------------------------------	-------------------------------------

MCyR is roughly corresponding to BCR-ABL1 levels $\leq 10\%$ (IS) (Ross et al 2009).

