5.4.2 Cytogenetic response

Cytogenetic response will be based on the percentage of Ph⁺ metaphases in the bone marrow. Cytogenetic evaluations will be considered for response assessment only if the number of metaphases examined is ≥ 20 in each bone marrow sample. As per protocol, fluorescent *in-situ* hybridization (FISH) assessments will not be considered for any evaluation of cytogenetic response during treatment.

Cytogenetic response is categorized as follows (a review of a minimum of 20 metaphases is required):

- Complete response (CCyR): 0% Philadelphia chromosome positive (Ph⁺) metaphases
- Partial response (PCyR): >0 to 35% Ph⁺ metaphases
- Major response (MCyR = CCyR + PCyR): 0 to 35% Ph⁺ metaphases
- Minor response (mCyR): >35 to 65% Ph⁺ metaphases
- Minimal response: >65 to 95% Ph⁺ metaphases
- None: >95 to 100% Ph⁺ metaphases.

If bone marrow aspirate blast percentage is provided as ‘ $<X$ ’ (i.e. below limit of detection), the numeric value is set to X for summary tables. In the listing ‘ $<X$ ’ will be presented.

Complete cytogenetic response (CCyR)

CCyR is defined as a value of 0% Ph⁺ metaphases in bone marrow.

CCyR will be considered as a binary variable with patients achieving CCyR grouped as ‘responders’ and patients not achieving CCyR, patients with missing cytogenetic evaluations grouped as ‘non-responders’.

Loss of CCyR

Loss of CCyR is defined as an increase in the Ph+ bone marrow cells to > 0%.

Loss of CCyR must have led to treatment discontinuation because of lack of efficacy (based on the “End of Treatment Phase Disposition” eCRF or “End of Treatment Disposition” eCRF during the Treatment switch phase with Subject status=“lack of efficacy” and Reason of treatment failure = “After start of therapy, loss of CHR, CCyR or PCyR”).

In addition, CML-related death or progression to AP or BC will be considered as loss of CCyR in any case (if they occurred on treatment).

Major cytogenetic response (MCyR)

MCyR is defined as a value of 0% to 35% Ph+ metaphases in bone marrow.

MCyR will be considered as a binary variable with patients achieving MCyR grouped as ‘responders’ and patients not achieving MCyR, patients with missing cytogenetic evaluations grouped as ‘non-responders’.

Loss of MCyR is defined as an increase in the Ph+ bone marrow cells to > 35%. For patients with response = PCyR, this would constitute loss of PCyR.

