5.4.4 Treatment Failure

The following events will constitute 'treatment failure', and are based on the ELN criteria ([Baccarani et al 2013](#)) defining failure of a second line treatment adapted to include discontinuation of randomized treatment as an event:

- No CHR or > 95% Ph+ metaphases at three months after initiation of therapy or thereafter
- BCR-ABL1 ratio > 10% IS and/or > 65% Ph+ metaphases at six months after initiation of therapy or thereafter
- BCR-ABL1 ratio > 10% IS and/or > 35% Ph+ metaphases at 12 months after initiation of therapy or thereafter
- Loss of CHR, CCyR or PCyR at any time after initiation of therapy
- Detection of new BCR-ABL1 mutations which potentially cause resistance to study treatment (T315I and V299L), at any time after initiation of therapy
- Confirmed loss of MMR in 2 consecutive tests
- New clonal chromosome abnormalities in Ph+ cells: CCA/Ph+: at any time after initiation of therapy

- Discontinuation from randomized treatment for any reason* (Note that Reason for treatment discontinuation="completed" doesn't indicate a premature treatment discontinuation)

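### Duration of CCyR: once a responder has reached MMR, cytogenetic loss is largely unobservable and censoring falls just before relapse, so the Kaplan-Meier proportions still in CCyR lean upward in each arm

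*Combined protocol and SAP*

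**What the plan says.** References are to the SAP as amended by addendum 1.0 of 14-Oct-2020.

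- **Events.** Section 2.7.1.2 ends CCyR at "the earliest date of loss of CCyR, progression to AP/BC, or CML-related death".
- **Loss of CCyR.** Section 5.4.2: "Loss of CCyR is defined as an increase in the Ph+ bone marrow cells to > 0" per cent. It adds that the loss must have led to discontinuation for lack of efficacy, with loss of CHR, CCyR or PCyR as the recorded reason. On-treatment AP/BC or CML-related death also counts.
- **Marrow schedule.** Section 2.7.1.2: "bone marrow aspirate for cytogenetic analyses will be performed as long as subjects have not achieved MMR". A patient in MMR with no marrow at a visit is counted as in CCyR.
- **Treatment failure.** Section 5.4.4 includes "Confirmed loss of MMR in 2 consecutive tests".
- **Data cut.** Section 2.1.1: "The efficacy assessments collected post-treatment failure, post-EoT or post S-EoT visit are not included in any efficacy analyses", OS and PFS excepted. Assessments on or before treatment failure are kept.
- **Censoring.** Section 2.7.3: event-free responders are "censored at the last cytogenetic assessment date on treatment or the last PCR evaluation on treatment indicating MMR", taking the later of the two dates.
- **Summary.** Section 2.7.2 reports Kaplan-Meier curves by arm and the proportions still in CCyR at 24, 48, 72 and 96 weeks. Non-key secondary endpoints get no confirmatory test.

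**The concern.** PCR is used in one direction only. It can establish CCyR (through imputation from MMR) and prolong it (through the censoring date), but short of AP/BC or CML death it cannot end it. Ending CCyR takes a marrow, and after MMR no scheduled marrow is planned.

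A patient who relapses after MMR would ordinarily cross the molecular threshold before the cytogenetic one. When loss of MMR is confirmed, the efficacy record closes, and the censoring date goes back to the last PCR still in MMR unless a later eligible marrow exists. The patients about to enter the period of higher risk are thus the ones who leave the risk set as censored. Kaplan-Meier assumes that censored patients have the same future risk as those who stay. Here they do not, and the durability figures in the study report would look better than they should.

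**Working it through.** **The plan's own figures.** The documents give no expected value for duration of CCyR. The only design figures that bear on it are the Week 24 MMR rates, 15% and 35%. These reproduce: with 2:1 allocation the pooled rate is (0.15 + 2 × 0.35)/3 = 0.2833, and

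n(control) = [1.960 × √(1.5 × 0.2833 × 0.7167) + 1.2816 × √(0.1275 + 0.2275/2)]² / 0.20² = 73.2, rounded up to 74.

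The total is 74 + 148 = 222, as stated in section 3.1. This shows only that the plan expects more MMR on asciminib at Week 24.

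**The rules applied to one patient.** A CCyR responder reaches MMR and scheduled marrows stop. PCR later rises above 0.1% with a five-fold increase and is confirmed: treatment failure. Marrow at the EOT visit, if later, is excluded. Even if it were included, a stop recorded as loss of MMR would not meet the reason required in section 5.4.2. Result: censored at the last PCR in MMR.

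**Size, under assumed inputs.** None of these is in the documents: f, the share of CCyR responders who reach MMR; a, the yearly rate of losing MMR; b, the yearly rate of losing CCyR after MMR is lost; c = 0.20, the yearly rate of losing CCyR without MMR. Losses are exponential, and T = 96/52 = 1.846 years. AP/BC, CML death and the discontinuation condition are left out.

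True proportion in CCyR at 96 weeks = f·G + (1 − f)·exp(−cT), where G = [b·exp(−aT) − a·exp(−bT)]/(b − a).

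Rule as written, with marrows at t₁ to t₄ = 24, 48, 72 and 96 weeks (t₀ = 0) and MMR patients at risk only while in MMR: the product over k of 1 − dₖ/rₖ, where dₖ = (1 − f)[exp(−c·tₖ₋₁) − exp(−c·tₖ)] and rₖ = f·exp(−a·tₖ) + (1 − f)·exp(−c·tₖ₋₁).

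Example with f = 0.6, a = 0.10, b = 1.5:
- G = (1.5 × 0.8314 − 0.10 × 0.0627)/1.4 = 0.8863, and exp(−cT) = 0.6913.
- True: 0.6 × 0.8863 + 0.4 × 0.6913 = 0.808.
- As written: dₖ/rₖ = 0.0363, 0.0353, 0.0343, 0.0333, so the product is 0.868.

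| f | a | b | True | As written | Excess (points) |
|---|---|---|---|---|---|
| 0.4 | 0.05 | 0.5 | 80.2% | 81.0% | 0.8 |
| 0.6 | 0.10 | 1.5 | 80.8% | 86.8% | 6.0 |
| 0.8 | 0.10 | 1.5 | 84.7% | 93.2% | 8.5 |
| 0.8 | 0.05 | 1.5 | 89.1% | 93.5% | 4.4 |
| 0.9 | 0.20 | 1.5 | 77.8% | 96.2% | 18.4 |

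A simulation of 100,000 responders per scenario, with 12-weekly PCR and 24-weekly marrows, gave an excess of 0.8 to 18.3 points over f = 0.4 to 0.9, a = 0.05 to 0.20 and b = 0.5 to 1.5. No scenario gave an understatement.

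**Between arms.** At equal loss rates the excess grows with f (6.0 against 8.5 points). If the arm with more MMR loses it at half the rate, the order reverses (4.4 against 6.0).

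**If some losses after MMR are still captured.** Take a second assumed set: 85% and 60% of responders reach MMR, every responder has a 10% true loss by 96 weeks, and uncaptured losses are censored 12 weeks early. True values are 90% in both arms. With none captured the rule gives about 98% and 96%. With half captured it still gives about 94% and 93%, and the spurious difference shrinks from about 2.5 to 1.3 points.

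**The case against.** The strongest replies, and what stands of each:

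- **Loss after MMR can still be recorded.** This stands. AP/BC and CML-related death are events for everyone, section 5.4.1 itself foresees loss of CCyR after MMR, and a marrow on or before treatment failure counts. A reader might infer that the plan cannot record loss at all; the documents do not support that. The remaining routes are narrow, because of both the data cut and the required discontinuation reason.
- **Marrows may resume once MMR is lost.** Protocol section 7.2.1.2, which would settle this, is not in the part available. If they do resume, those taken after confirmed loss of MMR are still excluded by section 2.1.1.
- **The arm direction is not established.** This stands. A reader might infer that asciminib is flattered most, but the loss rates by arm are not given. Nor does the plan assume 53% against 30% MMR at Week 96: in section 3.2, 53% is the detectable rate at 90% power, and only the 30% on bosutinib is anticipated.
- **The SAP does not tie loss of CCyR to 1% IS.** This stands. The entry "BCR-ABL1 <1% and/or Ph+ 0" in section 5.1.2.1 is a six-month milestone, cited to support imputing major response at 10% or below. A single PCR above 1% is therefore unsuitable as the main definition, and it misses patients stopped between 0.1% and 1%.
- **The calculation leaves out the discontinuation condition.** This stands. That condition also suppresses events in patients without MMR, so the contrasts shown are illustrative.
- **The relapses appear elsewhere.** This stands. Confirmed loss of MMR is an event in duration of MMR and in time to treatment failure, which limits the harm but does not correct this endpoint.

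**Conclusion.** The concern holds as an upward bias within each arm. For CCyR responders who reach MMR, cytogenetic loss is largely, though not wholly, unobservable, and the censoring date typically falls just before relapse. The sections cited produce this when followed as written.

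The size cannot be fixed from the documents. About 1 to 18 points at 96 weeks is an illustration that depends on the share of responders reaching MMR, how fast MMR is lost, and how soon CCyR follows. No conclusion about which arm gains more is warranted without arm-specific loss rates.

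Duration of CCyR is descriptive and outside the confirmatory tests, so inference on MMR at 24 and 96 weeks is untouched. The change is still worth making, because per-arm durability figures will be read side by side.

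**What to change.** For duration of CCyR only:

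1. In sections 2.1.1 and 2.7.3, use marrow and PCR data up to and including the EOT visit instead of cutting at an earlier treatment-failure date. In section 5.4.2, let an EOT marrow with Ph+ above 0% count as loss of CCyR even when the recorded discontinuation reason is loss of MMR.
2. Add two sensitivity analyses for responders with no marrow after MMR. In the first, confirmed loss of MMR ends CCyR. This is a worst case, since loss of MMR is not itself loss of CCyR: in the example above it gives 0.6 × 0.8314 + 0.4 × 0.6913 = 77.5%, against a true 80.8%. In the second, an on-treatment PCR above 1% IS is the loss event and censoring is at the last PCR at or below 1% IS.
3. Report by arm how many responders had CCyR imputed from MMR and how many were censored at a PCR date.

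The cost is SAP wording, one further derivation and two sensitivity runs on data already collected. The drawbacks are a molecular surrogate in the sensitivity analyses and less favourable durability figures. Addendum 1.0 already postdates the primary database lock, so the change should be dated and labelled as made after that lock.

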2.1 Data analysis general information

The planned analyses will be performed by Novartis and/or a designated CRO. SAS version 9.4 or later will be used to perform all data analyses and to generate tables, figures and listings.

There is no planned interim efficacy analysis. Prior to the database lock for the primary analysis, tables and figures aggregated by treatment arm for safety data review by the data monitoring committee or for other reporting activities will be produced by an independent statistician and independent statistical programmers.

For between-treatment comparisons of efficacy endpoints, randomization stratification factor, i.e. cytogenetic response status (MCyR vs no MCyR) at screening, will be included in respective stratified statistical tests.

Data included in the analyses

The analysis data cut-off dates for the planned analyses are:

- Primary analysis: After all randomized patients have been on study treatment for 24 weeks or discontinued earlier, i.e., LPFT + 24 weeks.
- 96-week analysis: After all randomized patients have been on study treatment for 96 weeks or discontinued earlier, i.e., LPFT + 96 weeks
- End of study treatment analysis: 30 days after the EOSt. (Note: After the study treatment period, the assigned study treatment will be made available, may be outside of this study, to patients who in the opinion of the investigators are still deriving clinical benefit.)
- PFS/OS update analysis: 5 years from the date when the last randomized patient received the first study dose (irrespective of treatment switch for patients failing bosutinib).

All statistical analyses will be performed using all data collected in the database up to the respective data cut-off date. All data with an assessment date or event start date (e.g. vital sign assessment date or start date of an adverse event) prior to or on the cut-off date will be included in the analysis. Any data collected beyond the cut-off date will not be included in the analysis and will not be used for any derivations.

All events with start date before or on the respective cut-off date and end date after the respective cut-off date will be reported as ongoing. The same rule will be applied to events starting before or on the respective cut-off date and not having documented end date. This approach applies, in particular, to adverse event and concomitant medication reports. For these events, the end date will not be imputed and therefore will not appear in the listings.

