of prior applicable visit" +1. "Upper limit" = "target day of current visit" + integer part of ("target day of next applicable visit" – "target day of current visit")/2.

Visit window for the switched treatment period will use the same rules as described above but with Day 1 being the date of first administration of asciminib. Visit name for the switched treatment period will be defined similarly with annotated by beginning with "S-" (e.g. S-Week 4) to differentiate from those used for the randomized treatment period.

Last contact date

The last contact date will be derived for patients not known to have died at the respective analysis data cut-off date using the last complete date among the following:

Table 2-5 Last contact date data sources

Source data	Conditions
Date of randomization	No condition
Last contact date/last date patient was known to be alive from Survival Follow-up page	Patient status is reported to be alive, lost to follow-up or unknown
Start/End dates from further antineoplastic therapy	Non-missing medication/procedure term
Start/End dates from drug administration record	Non-missing dose. Doses of 0 are allowed
End of treatment date from end of treatment page	No condition
Any specific efficacy (molecular or cytogenetic) assessment date if available	Evaluation is marked as 'done'
Laboratory/PK collection dates	Sample collection marked as 'done'
Vital signs date	At least one non-missing parameter value
Performance status date	Non-missing performance status
Start/End dates of AE	Non-missing verbatim term

The last contact date is defined as the latest complete date from the above list on or before the respective data cut-off date. The cut-off date will not be used for last contact date, unless the patient was seen or contacted on that date. No date post the cut-off date will be used. Completely imputed dates (e.g. the analysis data cut-off date programmatically imputed to replace the missing end date of a dose administration record) will not be used to derive the last contact date.

The last contact date will be used for censoring of patients in the analysis of overall survival.

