2.7.1.3 Other secondary efficacy endpoints

Time to treatment failure (TTF) is defined for patients in FAS as the time from date of randomization to an event of treatment failure. The events that constitute ‘treatment failure’ are described in the Appendix. They are based on the ELN criteria [[Baccarani et al. 2013](#)] defining failure of a second line treatment adapted to include discontinuation of randomized treatment as an event.

TTF (in months) is calculated as: (date of treatment failure or censoring date (see [Section 2.7.3](#)) - date of randomization + 1)/30.4375.

Progression-Free-Survival (PFS) is defined for patients in FAS as the time from the date of randomization to the earliest occurrence of documented disease progression to AP/BC or the date of death from any cause (including progressions and deaths observed during the survival follow-up period).

PFS (in months) is calculated as: (date of disease progression/death or censoring date (see [Section 2.7.3](#)) - date of randomization + 1)/30.4375.

Overall survival (OS) is defined for patients in FAS as the time from the date of randomization to the date of death (including the survival follow-up period).

OS (in months) is calculated as: (date of death or censoring date (see [Section 2.7.3](#)) - date of randomization + 1)/30.4375, regardless whether the patient switched from bosutinib to asciminib.

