3.1 Primary analysis

To test the null hypothesis that the MMR rate at 24 weeks is equal in the two treatment arms, based on two-sided 5% level of significance and with 90% power, 222 patients will be needed in total (i.e. 148 patients in the asciminib arm and 74 patients in the bosutinib arm based on 2:1 randomization allocation). The calculations were made using the software package PASS (2008).

It is assumed that asciminib leads to a 20% improvement in the MMR rate at 24 weeks over bosutinib from 15% to 35% which corresponds to an odds ratio of 3.05. The assumed bosutinib MMR rate of 15% at 24 weeks is based on previous trials evaluating bosutinib therapy ([Kuoury et al. 2012], [Gambacorti-Passerini et al. 2014], [García-Gutiérrez et al. 2015]).

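### PFS counts events through survival follow-up but stops event-free time at the last disease assessment, so late PFS estimates can be too low in both arms

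*Combined protocol and SAP*

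**What the plan says.** SAP 2.7.1.3 defines PFS from randomization to progression to accelerated phase or blast crisis (AP/BC) or death from any cause, "including progressions and deaths observed during the survival follow-up period". Under SAP 2.7.3, if no event has occurred, "their PFS times will be censored at the date of last study assessment (PCR, cytogenetic, hematologic or extramedullary) before the cut-off date". This holds whatever therapy the patient goes on to receive, a switch to asciminib included. A survival follow-up contact is not on that list of assessments.

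Overall survival is handled differently. It is censored at last contact, and the sources in Table 2-5 (SAP 2.1.1) include the "Last contact date/last date patient was known to be alive from Survival Follow-up page".

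Three other provisions matter:

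- SAP 2.1 sets the "PFS/OS update analysis: 5 years from the date when the last randomized patient received the first study dose". SAP 2.7.2 reports Kaplan-Meier PFS at 1, 3 and 5 years with a stratified Cox hazard ratio.
- SAP 1.1 ends study treatment 96 weeks after the last patient's first treatment (LPFT), or 48 weeks after the last switch from bosutinib to asciminib if that is later. Switching is open for 96 weeks after the last randomization.
- SAP 2.1.1 keeps efficacy assessments made after treatment failure or after the end-of-treatment visit out of all efficacy analyses other than PFS and OS.

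**The concern.** Take two patients who have both stopped treatment and are followed for survival only. One dies in year 4 and contributes four years and an event. The other is confirmed alive in year 4 without AP/BC but had the last PCR in year 1; this patient contributes one year and leaves the risk set. Off-treatment time is kept when it ends badly and discarded when it does not. Kaplan-Meier and Cox estimates both require that censoring carry no information about the outcome, and here it does.

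At stake are the 3- and 5-year PFS rates and the PFS hazard ratio. The final planned analysis consists only of PFS and OS (SAP 2.15), so PFS is half of what it delivers.

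**Working it through.** **The plan's own figures.** The documents give no PFS rate, event count or discontinuation rate to reproduce. The one design calculation is for the primary endpoint: "based on two-sided 5% level of significance and with 90% power, 222 patients will be needed in total", with MMR "from 15% to 35% which corresponds to an odds ratio of 3.05" and "148 patients in the asciminib arm and 74 patients in the bosutinib arm based on 2:1 randomization allocation". With p̄ = (2×0.35 + 0.15)/3 = 0.283, the bosutinib arm needs [1.960√(1.5×0.283×0.717) + 1.282√(0.35×0.65/2 + 0.15×0.85)]²/0.20² = 73.2, so 74, and 148 on asciminib. It reproduces, and it fixes the 2:1 allocation used below.

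**Time between the two windows.** Study treatment ends at the latest about 96 + 48 = 144 weeks after LPFT. Events count to LPFT + 5 years, about 261 weeks. The gap is at least 261 − 144 = 117 weeks, and 261 − 96 = 165 weeks if treatment ends at the earlier date.

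**Assumptions, none from the documents.** Exponential PFS, identical in both arms, with true 5-year PFS 85% (λ = −ln 0.85/5 = 0.0325 per year); uniform 2-year accrual; complete ascertainment of events; discontinuation by week 96 of 30% on asciminib and 60% on bosutinib, independent of PFS; end of study treatment at LPFT + 96 weeks.

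**Hand check, no off-treatment assessments.** The first patient enrolled reaches end of study treatment at 2 + 1.84 = 3.84 years. Beyond that, every event-free patient is already censored, and the risk set contains only patients who will have an event before cut-off. Cut-off falls at c years after entry, uniform on 5 to 7. The mean of e^(−λc) is (0.850 − 0.7965)/(2×0.0325) = 0.823. The curve therefore falls between 3.84 and 5 years by the factor (0.850 − 0.823)/(0.883 − 0.823) = 0.0270/0.0597 = 0.453. The estimate at 3.84 years cannot exceed the true 0.883, so the 5-year estimate cannot exceed 0.883 × 0.453 = 40%, whatever the discontinuation rates. With treatment ending at LPFT + 144 weeks (4.76 years) the same steps give at most 0.857 × (0.0270/0.0337) = 0.857 × 0.802 = 69%. The truth is 85%.

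**Large-sample simulation, asciminib / bosutinib (truth 91% at 3 years, 85% at 5 years).**

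| Assessed to cut-off | Discontinuation by week 96 | 3-year KM | 5-year KM |
|---|---|---|---|
| none | none | 89% / 89% | 35% / 36% |
| none | 30% / 60% | 86% / 80% | 33% / 28% |
| half | 30% / 60% | 89% / 88% | 79% / 78% |
| 80% | 30% / 60% | 90% / 90% | 83% / 83% |
| all | 30% / 60% | 91% / 91% | 85% / 85% |

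The 1-year estimate is off by less than 1.5 points throughout. With no off-treatment assessments and 30% / 60% discontinuation, the 5-year estimate is 39% / 37% for a truth of 95%, 28% / 24% for a truth of 75%, and 54% / 42% for a truth of 85% with 3-year accrual. With treatment ending at LPFT + 144 weeks and a truth of 85%, it is about 59%, 50% and 38% for 0%, 30% and 60% discontinuation.

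**Hazard ratio, asciminib over bosutinib, true value 1, no assessments after treatment.**

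| Discontinuation | Bosutinib discontinuers who switch and stay assessed | HR |
|---|---|---|
| 30% / 60% | 0% | 0.80 |
| 30% / 60% | 30% | 0.90 |
| 30% / 60% | 50% | 0.96 |
| 30% / 60% | 100% | 1.12 |
| 45% / 45% | 0% | 0.99 |
| 60% / 30% | 0% | 1.27 |

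At a cut-off of LPFT + 96 weeks, 30% / 60% gives 0.67 without switching and 0.84 with 30% switching.

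**The two repairs under 30% / 60%.** Censoring at last contact, with status fully known, gives 85% / 85% at 5 years and HR 1.00. Counting events only up to the last assessment gives 88% / 89%, from a sparse tail, and HR 1.00.

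**The case against.** Censoring PFS at the last disease assessment is a familiar convention, because freedom from progression is known only when someone has looked. That is fair, but the convention is coherent only when events are tied to the same assessments. Here deaths and progressions count without any time limit after the last one.

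The stronger objection is that the available text does not say assessments stop with treatment. The visit schedule is not in the part available, SAP 2.1.1 admits post-treatment assessments into PFS, and treatment after end of study treatment only may be outside the study. This stands: the size of the error is conditional, and the 28-36% figures are the extreme. But SAP 2.1.1 permits those assessments without scheduling them, and with half of the patients still assessed the 5-year estimate remains 6 to 7 points low.

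A reader might infer that all event-free patients are censored by LPFT + 96 weeks. The documents do not support that: a late switch can move end of study treatment to about LPFT + 144 weeks, which reduces the error without removing it.

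A reader might also infer that the rule tilts the hazard ratio against bosutinib. That needs earlier loss of assessments on bosutinib, and no discontinuation or switching rates are given. Only bosutinib patients can switch, and their assessments on asciminib postpone censoring; this shrinks the tilt and can reverse it.

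**Conclusion.** The mismatch between the event window and the censoring window is in the text and does not depend on any assumption. Its effect on late PFS needs no difference between arms, because even with no early discontinuation all event-free time stops well before events do. How large it is depends mainly on how completely patients are assessed off treatment: under the stated assumptions, from about 50 points or more at 5 years with none to zero with all. The 3-year rate is affected less and the 1-year rate hardly at all.

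For the hazard ratio, the supportable statement is that it is distorted whenever loss of assessments differs between arms. A direction cannot be claimed. PFS carries no confirmatory test (SAP 2.7.2), so the primary and key secondary tests and the sample size are untouched. The point is still worth settling before the 5-year update, and preferably before the 96-week analysis.

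**What to change.** In SAP 2.7.3, use one window for events and censoring.

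- **Main rule:** censor event-free patients at the last date they were documented alive and free of AP/BC, up to the cut-off, including survival follow-up contacts that record progression status. Do not take every Table 2-5 date: an adverse event date, or a contact with status unknown, does not show freedom from AP/BC.
- **Sensitivity analysis:** count events only within a fixed, pre-stated interval after the last disease assessment, and censor the rest at that assessment.
- **If follow-up contacts do not record progression status,** make the second rule the main analysis.
- **Report completeness of follow-up by arm,** showing how long disease assessments continued after treatment.

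The cost is a short SAP change and a little extra programming. The second rule drops late events: in the simulation with 35% / 50% discontinuation, expected events among 222 patients fell from 39 to 14 when only events up to the last assessment counted. If off-treatment assessments prove complete, the main rule changes nothing.
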